8.4.1. Specific criteria for withdrawal (if applicable)

Not applicable for this study.

8.5. REPLACEMENT OF INDIVIDUAL SUBJECTS AFTER WITHDRAWAL

No new subjects will be included for each withdrawn subject. In our power calculation for the sample size, we have taken into account 30% attrition.

8.6. FOLLOW-UP OF SUBJECTS WITHDRAWN FROM TREATMENT

If a subject decides to withdraw from the study, the investigator will ask for the reason. It will be enquired whether the subject wishes to withdraw from the study or from a specific time point only and so whether the subject can be re-contacted at a later time. Withdrawal from the study will have no effect on the regular treatment. Subjects who leave the study for medical reasons will be followed until the interfering condition has resolved or reached a stable state.

8.7. PREMATURE TERMINATION OF THE STUDY (IF APPLICABLE)

Not applicable.

9. SAFETY REPORTING

9.1 TEMPORARY HALT FOR REASONS OF SUBJECT SAFETY

The study sponsor (UNIVR) will suspend the study if there is sufficient ground that continuation of the study will jeopardize subject health or safety. The sponsor will notify the Ethics Committee without undue delay of a temporary halt including the reason for such an action. The study will be suspended pending a further positive decision by the Ethics Committee. The investigator will take care that all subjects are kept informed.

9.2 AES AND SAES

9.2.1 ADVERSE EVENTS (AES)

Adverse events are defined as any undesirable experience occurring to a subject during the study, whether or not considered related to the trial procedure or the stepped-care DWM/PM+ intervention. All adverse events reported spontaneously by the subject or observed by the investigator or his staff will be recorded.

9.2.2 SERIOUS ADVERSE EVENTS (SAES)

A serious adverse event is any untoward medical occurrence or effect that

- results in death;
- is life threatening (at the time of the event);
- requires hospitalization or prolongation of existing inpatients' hospitalization;
- results in persistent or significant disability or incapacity;
- is a congenital anomaly or birth defect; or
- any other important medical event that did not result in any of the outcomes listed above due to medical or surgical intervention but could have been based upon appropriate judgement by the investigator.

An elective hospital admission will not be considered as a serious adverse event.

The investigator will report all SAEs to the sponsor without undue delay after obtaining knowledge of the events.

9.3 FOLLOW-UP OF ADVERSE EVENTS

All AEs will be followed until they have abated, or until a stable situation has been reached.

Depending on the event, follow-up may require additional tests or medical procedures as indicated, and/or referral to the general physician or a medical specialist. SAEs need to be reported till end of study. The DWM and PM+ helpers will be supervised and receive weekly supervision by experienced mental health care professionals. If, during the course of the study, participants in the treatment group (PM+/DWM/CAU) or comparison group (CAU only) show severe psychiatric symptoms (e.g., psychosis, imminent suicide risk, etc.), or any other symptoms occur that require immediate specialist treatment and follow-up, they will be referred to specialist staff (e.g. psychiatrists) for immediate follow-up. The researcher from UNIVERSITY OF VERONA will be responsible to monitor this process and make sure the appointment has been made.

9.4 ETHICS AND DATA ADVISORY BOARD (EDAB)

The RESPOND' Ethics and Data Advisory Board (EDAB) will monitor and provide expert advice on data management and all ethical, legal and societal issues that arise within the project, promoting integrity and a better alignment of RESPOND with social needs and expectations that may arise within or as a result of RESPOND. This includes monitoring

the safety, rights, and wellbeing of study participants, and providing input for ethics reports. In addition, the EDAB will provide advice on FAIR data management, including data privacy and adherence to the GDPR. The EDAB will ensure that the trial and data collection in RESPOND are conducted in accordance with the International Conference on Harmonisation (ICH), the WHO Good Clinical Practice standards (GCP), Declaration of Helsinki (64th WMA General Assembly, Fortaleza, Brazil, October 2013), and (inter)national laws (e.g. Medical Research Involving Human Subjects Act (WMO)). In addition, the ethical, legal of the participants and research staff members will be reviewed and interim analyses will be considered in case safety issues are (suspected to be) violated. Incidental findings within RESPOND refer to an extreme score on study instruments (questionnaires or interviews) that need additional follow-up. Other issues that will be considered include privacy and intellectual property rights. Relevant issues will be discussed in an annual meeting, but if issues arise between these meetings, the EDAB will be requested to plan an additional meeting. Additional meetings will be held before submission of ethics documents for formal approval as well as before submission of ethics reports. The EDAB comprises of independent members having no conflict of interest with the sponsor of the study, i.e. dr. [name], dr. [name], and dr. [name], member of the Ethics Review Committee Board member (VUA). For RESPOND principal investigator Prof. dr. [name] will join the EDAB meetings together with assistant professor [name]. [name] LL.M (VU) will join for matters of data protection and privacy.

The management team and EDAB will ensure that all necessary actions will be undertaken to minimize risks and suggest necessary measures to counter these risks. Through efficient communication between the EDAB, overall management (Work Package 1), and leader of individual Work Packages, the consortium will ensure that mitigation measures will be undertaken in a timely and effective manner.

The advice(s) of the EDAB will only be sent to the sponsor of the study. Should the sponsor decide not to fully implement the advice of the EDAB, the sponsor will send the advice to the reviewing Ethics Committee, including a note to substantiate why (part of) the advice of the EDAB will not be followed. The EDAB should conclude each review with their recommendations to RESPOND as to whether the study should continue without change, be modified, or be terminated. Recommendations regarding modification of the design and conduct of the study could include: modifications of the study protocol based upon the review of the safety data; suspension or early termination of the study or of one or more study arms because of serious concerns about subjects' safety, inadequate performance, or rate of enrolment; suspension or early termination of the study or of one or more study arms because study objectives have been obtained according to pre-established statistical guidelines.

10. STATISTICAL ANALYSIS

The statistical analyses for the Randomized Controlled Trial are described under section below.

10.1 PRIMARY OUTCOME(S)

The statistical analysis of the RCT will estimate effectiveness of the stepped-care DWM/PM+ with PFA and CAU intervention compared to PFA and enhanced CAU alone, with PHQ-ADS score as the primary study outcome.

The primary outcome will be summarized using number of subjects (n), minimum and maximum; and means, standard deviations (SD) for normally distributed data, or medians and inter-quartile ranges for non-normally distributed data. To measure comparisons at baseline between the two treatment groups t -tests (continuous variables) or chi-squared test (categorical variables) will be conducted for normally distributed data; Mann-Whitney tests will be conducted for continuous non-normally distributed data.

Both intention-to-treat (ITT) analysis, including all randomized participants ($n=212$), and completers' (per protocol - PP) analysis will be carried out. The main conclusion of the trial will be based on the ITT analysis of the primary outcome. A secondary analysis of the primary outcome will also be presented using the PP population.

The statistical analysis will be masked, i.e. the trial statistician will be blinded to the treatment groups until the analysis has been completed. Moreover, the trial statistician will not be involved in determining participants' eligibility, in administering the intervention, in measuring the outcomes or in entering data.

To estimate the treatment effect, a linear mixed model will be employed for the primary endpoint analysis, which will have treatment as fixed effects, baseline measurement of primary endpoint as covariate, and subject as random effects. The mean difference between two treatment arms at each visit/time together with its 95% confidence interval will be derived from the mixed model. Covariate-adjusted mixed model of primary endpoint will also be performed by adding pre-specified covariates at baseline (gender, age, education, prior trauma, COVID-19 related events and stressor list) into the above model.

Missing data

Missing data will be treated as missing at random (MAR). No imputations of missing values will be made, as multilevel models can deal with missing data (Singer, Willett & Willett, 2003).

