6.4. SAMPLE SIZE CALCULATION

A total number of 212 participants will be included. Based on prior studies on a PM+ intervention (Bryant et al., 2017; Rahman et al., 2016b), we aim to detect a small to medium effect size Delta (defined as the square root of the ratio of the variance of the tested effect to the comparison error variance) of 0.3 in the PM+ group at 2 months post-treatment based on the primary composite outcome PHQ-ADS (Kroenke et al., 2016; 2019). The PHQ-ADS is the combined sum score of depression and anxiety symptoms of the PHQ-9 and GAD-7, respectively and has shown good internal consistency ($\alpha = .88$ to $.92$) (Kroenke et al., 2016; 2019). A power calculation for an ANOVA repeated

measurement design with two time-periods to identify the effect of treatment at the last endpoint suggests a minimum sample size of $N=74$ per group (power=0.95, $\alpha=0.05$, two-sided, $\rho=0.9$). Taking into account 30% attrition, we aim to include a total number of 212 participants (106 in the stepped-care DWM/PM+ treatment group - with PFA and CAU - and 106 in the PFA and CAU comparison group).

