8.1.1. Main study parameter/endpoint

The primary endpoint will be the decrease in symptoms of depression and anxiety from baseline to two-month follow-up after the PM+ intervention ended, measured through the combined sum score of the Patient Health Questionnaire-9 (PHQ-9) and Generalized Anxiety Disorder (GAD-7) previously validated as the PHQ-ADS (Kroenke et al., 2016; 2019). A description of the measure(s) can be found under 'Study Procedures'. Based on prior studies on PM+ in Pakistan and Kenya (Rahman et al., 2016b; Bryant et al., 2017) where PM+ was administered as a standard treatment, we expect to detect a Cohen's *d* effect size of 0.3 in the PM+ group at 2 months post-treatment.

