10.2 SECONDARY OUTCOME(S)

Economic outcomes

Health economic analysis will be conducted to determine the difference in costs and outcomes in the intervention arm as compared to the care as usual group at each time-point. Primary analysis will be the total costs over the 2-month follow-up treatment period. Between-group comparison of mean costs will be completed using standard t-test with ordinary least squares regression used for adjusted analysis, with the validity of results confirmed using bootstrapping. Pseudonymised data will be sent to the London School of Economics and Political Science, partner in RESPOND under Work Package 3, for the health economics analysis of the CSRI.

Analysis of secondary outcomes with repeated measurements

Additionally, a linear mixed model as mentioned for the primary outcome analysis (PHQ-ADS) will be carried out for analyzing the following clinical outcomes measured at baseline, at 2 weeks after DWM, at 1 week and at 2 months after finishing PM+: posttraumatic stress reactions (PCL-5), depressive symptoms (PHQ-9), generalized anxiety (GAD-7), resilience (MIMIS) and quality of life (EQ-5D-5L).

Analysis of other secondary outcomes

Changes in caseness of the composite measure anxiety and depression will be calculated using the recommended cut-off of >20 for moderate severity on the PHQ-ADS questionnaire (Kroenke et al., 2016; Kroenke et al., 2019) and will be analyzed using a hierarchical logistic model with the same fixed and random effects as the hierarchical linear models above, from which odds ratio of having a depression together with 95% CI at each time point will be derived.

Corrections for multiple testing

Models will be tested on $\alpha = .05$; to deal with problems associated with multiple testing, for each time point T2-T4 the hypothesis that the experimental intervention has no effect on secondary outcome scores will be tested by performing the Seemingly Unrelated Regression equations model (Zellner, 1962), controlling for baseline values.

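### The terms listed for the primary mixed model give one pooled treatment difference, so they cannot give the per-visit differences promised next or the T4 difference that is the primary endpoint

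*Protocol*

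**What the plan says.** **Model terms.** Protocol section 10.1 describes the linear mixed model for the primary endpoint as one "which will have treatment as fixed effects, baseline measurement of primary endpoint as covariate, and subject as random effects". The covariate-adjusted version adds baseline characteristics only. Section 10 contains no visit term and no treatment-by-visit term.

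**Promised output.** The next sentence of 10.1 reads: "The mean difference between two treatment arms at each visit/time together with its 95% confidence interval will be derived from the mixed model".

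**Endpoint and sizing.** Section 8.1.1 sets the primary endpoint as the "decrease in symptoms of depression and anxiety from baseline to two-month follow-up after the PM+ intervention ended", which is T4 in section 8.1. The power calculation in section 6.4 is meant "to identify the effect of treatment at the last endpoint suggests a minimum sample size of" 74 per group, so it also targets the final time point.

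**Reuse in 10.2.** The caseness analysis is a "hierarchical logistic model with the same fixed and random effects as the hierarchical linear models above", from which the "odds ratio of having a depression together with 95% CI at each time point will be derived". The continuous secondary outcomes reuse the primary model. They also have a separate Seemingly Unrelated Regression step in which "for each time point T2-T4 the hypothesis that the experimental intervention has no effect on secondary outcome scores will be tested".

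**The concern.** The listed terms and the promised output do not fit each other. An analyst who fits the stated terms gets one treatment effect pooled over T2, T3 and T4. An analyst who reports differences by visit must add terms that the protocol does not state. Section 10.1 rests the main conclusion of the trial on this analysis (in the ITT population), so the choice bears directly on the confirmatory result.

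The pooled effect equals the T4 effect only if the treatment effect is the same at all three visits, and the design makes that an unsafe default. T2 falls two weeks after DWM and decides who goes on to PM+, so nobody in the treatment arm has had step 2 by then. A pooled coefficient mixes an effect of DWM alone with effects measured after the full programme, and it can miss the T4 effect in either direction.

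**Working it through.** **1. The sample size already targets T4.** Inputs from section 6.4: Delta = 0.3 (a variance-ratio effect size), two-sided alpha 0.05, power 0.95, 30% attrition. Using a noncentral F on 1 and 2n - 2 degrees of freedom with noncentrality 2n x 0.3^2:
- n = 73 gives power 0.9496 and n = 74 gives 0.952, so 74 per group is reproduced.
- 74 / 0.70 = 105.7, so 106 per group and 212 in total.

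No sample-size figure is in dispute on this point.

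**2. What the listed model can estimate.** Its mean for subject i at visit j is

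E(Y_ij) = a + t x treatment_i + b x baseline_i

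The right-hand side does not depend on j. There are three fixed parameters, and the difference between arms is t at T2, T3 and T4 alike. The random subject effect has mean zero and does not change this. Fitting T4 alone does not rescue the text: with one record per subject the random intercept cannot be separated from the residual, and the text promises every visit.

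**3. What the pooled coefficient averages.** Assumptions, not in the protocol: unit variance; a common correlation rho between all visits, baseline included; monotone dropout, equal in both arms, cumulative 15/22/30% at T2/T3/T4. Only the overall 30% attrition is stated. Conditional on baseline:
- total variance = 1 - rho^2
- between-visit covariance = rho - rho^2 = rho(1 - rho)
- residual variance = (1 - rho^2) - (rho - rho^2) = 1 - rho

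Under generalised least squares, each observation from a subject with k visits has weight 1 / [(1 - rho) + k x rho(1 - rho)]. At rho = 0.5:

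| Visits observed (k) | Proportion | Weight per observation |
|---|---|---|
| 1 (T2 only) | 0.85 - 0.78 = 0.07 | 1/0.75 = 1.333 |
| 2 (T2, T3) | 0.78 - 0.70 = 0.08 | 1/1.00 = 1.000 |
| 3 (T2 to T4) | 0.70 | 1/1.25 = 0.800 |

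- T2: 0.07 x 1.333 + 0.08 x 1.000 + 0.70 x 0.800 = 0.733
- T3: 0.08 x 1.000 + 0.70 x 0.800 = 0.640
- T4: 0.70 x 0.800 = 0.560
- Sum 1.933, so the weights are 0.379 / 0.331 / 0.290.

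Sensitivity:

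| Setting | T2 | T3 | T4 |
|---|---|---|---|
| 15/22/30%, rho 0.3 | 0.375 | 0.332 | 0.293 |
| 15/22/30%, rho 0.5 | 0.379 | 0.331 | 0.290 |
| 15/22/30%, rho 0.7 | 0.382 | 0.330 | 0.288 |
| 15/22/30%, rho 0.9 | 0.385 | 0.329 | 0.286 |
| No dropout | 0.333 | 0.333 | 0.333 |
| 5/10/30%, rho 0.5 | 0.385 | 0.354 | 0.261 |

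**4. Consequence for illustrative effect paths** (SD units, rho 0.5, 15/22/30% dropout). For example, 0.1 x 0.379 + 0.2 x 0.331 + 0.3 x 0.290 = 0.191. The last two columns are means over 4000 simulated trials with 106 per arm and known variance components (Monte Carlo SE 0.002).

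| True T2/T3/T4 | Pooled, formula | Pooled, simulated | T4 contrast once visit and treatment-by-visit are added |
|---|---|---|---|
| 0.1/0.2/0.3 | 0.191 | 0.193 | 0.303 |
| 0.1/0.3/0.3 | 0.224 | 0.223 | 0.300 |
| 0.2/0.3/0.3 | 0.262 | 0.261 | 0.301 |
| 0.3/0.3/0.3 | 0.300 | 0.302 | 0.302 |
| 0.5/0.4/0.3 | 0.409 | 0.408 | 0.297 |
| 0.3/0.15/0 | 0.163 | 0.163 | -0.002 |

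In the last row there is no effect at T4, yet the listed model estimates 0.16.

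**The case against.** The strongest reply is that the term list is not declared exhaustive. Adding visit and treatment-by-visit contradicts no word of it, the sentence about per-visit differences shows that time terms were intended, and model terms are often completed in an SAP. It is true that the intent is probably recoverable, which is why the correction is small. But the protocol did choose to state the terms by role, and section 10.2 then carries them forward as the same fixed and random effects. Nothing in section 10 adds time. A stated specification that cannot give its stated output is wrong text, not detail left for later.

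Two further points have some force. First, sections 6.4 and 8.1.1 identify T4, so a careful reader can work out which contrast is primary. Naming it in 10.1 removes doubt but is the lesser part of the point. Second, the size of any bias depends on assumed effect paths and an assumed dropout split, and it is zero under a constant effect. That stands: the figures show a possible range, not an expected error.

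The matter in 10.2 follows from the same wording and is not a separate defect. For the continuous secondary scores the per-time-point regression tests soften the consequence, but they do not cover the primary outcome.

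**Conclusion.** The concern holds. As written, the primary model estimates one treatment effect averaged over T2 to T4. It cannot deliver the per-visit differences that 10.1 promises or the T4 effect that the trial is designed and sized to detect. That conclusion follows from the terms alone.

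The practical size is conditional. T4 would carry about 0.26 to 0.33 of the weight in the settings examined, so roughly 70% of the estimate would come from earlier visits. With a true T4 effect of 0.30 SD, the illustrative paths give pooled values from 0.19 to 0.41, and 0.30 when the effect is constant. These values rest on an exchangeable correlation, monotone dropout equal in both arms, and assumed T2 and T3 effects. The text should be corrected. The endpoint, its time point and the sample size are not in question.

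**What to change.** Replace the two sentences in section 10.1 with wording such as:

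> The model will include fixed effects for treatment, visit (T2, T3, T4, categorical) and treatment-by-visit, with baseline PHQ-ADS as covariate and a random effect for subject. Treatment differences with 95% CIs will be estimated at every visit; the primary test is the treatment contrast at T4.

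Some treatment-by-time term is essential. Coding visit as categorical is the natural choice with three visits, but it is a choice. Carry the same fixed effects into the secondary linear models and the logistic caseness model in section 10.2, which follow by reference. The covariance structure and any baseline-by-visit term can be left to the SAP.

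The cost is two sentences. The figures of 74 per group and 212 in total stay as they are, because section 6.4 already targets the last time point.

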8. METHODS

8.1. STUDY PARAMETERS/ENDPOINTS

All participants will have five assessments (T0-T4), mostly by filling out online questionnaires. The five assessments take place at the following time-points (see also Figure 1):

T0: Screening for eligibility including psychological distress

T1: Baseline assessment

T2: 2 weeks post DWM intervention assessment

T3: 1-week post PM+ intervention assessment

T4: 2-months post PM+ intervention assessment

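### The primary mixed model, read in the ordinary way, applies a variance pooled over T2–T4 to the T4 contrast, so the T4 interval is right only under an equal-variance assumption that the protocol does not support

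*Protocol*

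**What the plan says.** Section 8.1.1 sets the primary endpoint as the "decrease in symptoms of depression and anxiety from baseline to two-month follow-up after the PM+ intervention ended", measured by PHQ-ADS. Section 8.1 labels that visit "T4: 2-months post PM+ intervention assessment". Follow-up measurements are at T2, T3 and T4.

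Section 10.1 analyses the endpoint with a linear mixed model having "treatment as fixed effects, baseline measurement of primary endpoint as covariate, and subject as random effects". It adds: "The mean difference between two treatment arms at each visit/time together with its 95% confidence interval will be derived from the mixed model". No other source of within-person dependence is named, and nothing is said about residual variances by visit.

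Section 10.2 reuses the model for PCL-5, PHQ-9, GAD-7, MIMIS and EQ-5D-5L: "a linear mixed model as mentioned for the primary outcome analysis (PHQ-ADS) will be carried out". It also carries the same fixed and random effects into a hierarchical logistic model for caseness. The significance level is 5% ("Models will be tested on $\alpha = .05"). For multiplicity across secondary outcomes, section 10.2 uses Seemingly Unrelated Regression at each time point, controlling for baseline.

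The only correlation in the protocol is in the two-period sample size calculation of section 6.4: "power=0.95, $\alpha=0.05$, two-sided, $\rho=0.9".

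**The concern.** A subject random intercept with independent residuals is compound symmetry. It estimates one total variance for the three follow-up visits and uses that value for each visit-specific contrast. An overall effect averaged over visits tolerates this well, but a contrast at one visit does not. If the variance at T4 differs from the average, the standard error of the primary contrast is wrong by the square root of the ratio.

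Equal variance cannot be taken for granted here. Baseline PHQ-ADS is a covariate, so the relevant quantity is what baseline leaves unexplained at each visit, and that depends on both the SD and the correlation with baseline at that visit. The visits are widely spaced. DWM lasts five weeks and T2 is two weeks later (week 5 + 2 = 7). PM+ adds five weekly sessions and T3 is one week later (about 7 + 5 + 1 = 13). T4 is two months after PM+ (about 7 + 5 + 9 = 21). Repeated symptom scores often correlate less with baseline as time passes, and SDs can move either way under treatment.

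At stake is the interval on which the main conclusion rests. Too narrow means false positives above 5%; too wide means lost power.

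**Working it through.** **Inputs from the protocol.** Alpha 0.05 two-sided, power 0.95, rho 0.9, Delta 0.3, 74 per group, 30% attrition, 212 in total (section 6.4); 1:1 allocation (section 8.2); model terms (section 10.1).

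**Inputs not in the protocol, assumed.** SD pattern over T2–T4, correlation of each visit with baseline, visit weeks 0/7/13/21, and monotone dropout completely at random.

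**1. The plan's own figure.** Section 6.4 defines Delta as "defined as the square root of the ratio of the variance of the tested effect to the comparison error variance". Using a noncentral F with 1 and N − 2 degrees of freedom and noncentrality N × Delta²: at 74 per group, 148 × 0.09 = 13.32 and power is 0.952; at 73 per group power is 0.9496. So 74 reproduces. Then 74 / 0.70 = 105.7, rounded up to 106 per arm, 212 in total. The checks below use 106 per arm.

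**2. Closed form, complete data, visit-specific baseline slopes.** With SD s_j and baseline correlation r_j, the residual variance at visit j is v_j = s_j²(1 − r_j²). The model uses the mean of the v_j; the truth at T4 is v_T4.

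SE ratio (model / true) = √(mean v / v_T4). Type I error = 2 × (1 − Φ(1.96 × ratio)).

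| Baseline correlation T2/T3/T4 | SD T2/T3/T4 | v_j | Mean | Ratio | Type I error |
|---|---|---|---|---|---|
| 0.7/0.6/0.5 | 1/1/1 | 0.51/0.64/0.75 | 0.633 | 0.919 | 7.2% |
| 0.8/0.7/0.6 | 1/1/1 | 0.36/0.51/0.64 | 0.503 | 0.887 | 8.2% |
| 0.6/0.5/0.4 | 1/1/1 | 0.64/0.75/0.84 | 0.743 | 0.941 | 6.5% |
| constant, any value | 1/1/1 | equal | – | 1.000 | 5.0% |
| 0.7/0.6/0.5 | 1.2/1.1/1.0 | 0.734/0.774/0.750 | 0.753 | 1.002 | 5.0% |
| 0.5 constant | 1.0/1.1/1.2 | 0.750/0.908/1.080 | 0.913 | 0.919 | 7.2% |
| 0.5 constant | 1.2/1.1/1.0 | 1.080/0.908/0.750 | 0.913 | 1.103 | 3.1% |

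The fifth row matters: fading correlation with a modestly falling SD cancels out.

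**3. Simulation under the null.** 4,000 trials per scenario, 106 per arm, REML random intercept with visit, treatment-by-visit and one baseline slope, |z| > 1.96 (Monte Carlo SE about 0.35 points). Visit and treatment-by-visit terms were added because differences at each visit cannot be obtained without them. T4 type I error:

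| Scenario | No dropout | 30% dropout by T4 |
|---|---|---|
| Constant rho 0.9, equal SD | 4.6% | 5.1% |
| Constant rho 0.5, equal SD | 4.7% | 4.8% |
| Correlation 0.7 per 7 weeks, equal SD | 8.5% | 8.5% |
| Correlation 0.9 per 7 weeks, equal SD | 10.5% | 11.7% |
| Constant rho 0.5, SD 1.0/1.1/1.2 | 7.8% | 7.9% |
| Constant rho 0.5, SD 1.0/1.15/1.3 | 8.2% | 8.5% |
| Constant rho 0.5, SD 1.2/1.1/1.0 | 2.8% | 3.0% |
| Constant rho 0.5, SD 1.3/1.15/1.0 | 2.7% | 2.3% |
| Correlation 0.7 per 7 weeks, SD 1.2/1.1/1.0 | 5.5% | 7.6% |

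The model-to-true SE ratio runs from about 0.80 to 1.16. Over the same scenarios the treatment effect averaged over visits stays between about 4.6% and 6.1%, so the problem is specific to the single-visit contrast.

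**4. Does the alternative work?** In a separate run of 800 trials (106 per arm, baseline correlations 0.7/0.6/0.5, about 30% dropout), the random intercept gave a mean SE of 0.122 against an empirical SD of 0.137 and rejected 8.1%. An unstructured covariance gave a mean SE of 0.135 and rejected 5.2% (Monte Carlo SE 0.8 points).

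**The case against.** **It is a matter for the SAP.** Section 10.1 does not say that the random effect is an intercept only or that residuals are independent with equal variance, and residual covariance is often settled in an SAP, which is not shown. This stands in part: the text does not exclude a further structure. But the protocol has not left the matter blank. It names one dependence term, derives intervals at each visit from that model, and carries the same random effects into a logistic model, where a conventional fit has no free residual covariance. An SAP that follows the text literally would fit a random intercept.

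**The direction is not known.** A reader might infer that the T4 interval is necessarily too narrow and the test above 5%. The documents do not support that. Pooling can push the T4 variance either way, and the protocol gives no PHQ-ADS SD for any visit and no correlations between T2, T3 and T4. Its single rho of 0.9 belongs to a two-period calculation; held constant with equal SDs it gives about 5%. This objection stands in full.

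**Stepped care does not settle it.** PM+ goes only to treated participants still above the K10 cut-off. That could shrink the spread at T4 as easily as widen it. It would also make covariance differ between arms, which a matrix common to both arms does not address. It gives a reason to doubt equal variance, but no direction.

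**The secondary outcomes are less exposed than they look.** Their multiplicity test is Seemingly Unrelated Regression at each visit, which does not pool variance over visits. Only their mixed-model estimates and intervals share the weakness.

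**Conclusion.** The point holds as a conditional one. On the ordinary reading of section 10.1, the primary T4 interval has its nominal coverage only if the residual variance at T4 equals the average over T2–T4. The protocol neither states nor supports that assumption.

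Under assumed patterns, type I error at T4 is about 7% to 12% if correlation with baseline fades or SD rises, about 5% if both are constant, and about 2% to 3% if SD falls while correlation stays constant. Fading correlation and falling SD together partly or wholly cancel. These figures rest on SDs, correlations, visit weeks and a dropout mechanism that are not in the document. They show how far the result can move, not where it will be. Neither a proven inflation of the error rate nor a proven understatement of the standard error is claimed. The change is still worth making because it removes the dependence on an unsupported assumption at almost no cost.

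**What to change.** In section 10.1, for the continuous outcomes, replace the subject random effect with an unstructured within-subject covariance over T2, T3 and T4, fitted by REML with Kenward-Roger degrees of freedom. List visit, treatment-by-visit and baseline-by-visit as fixed effects with treatment and baseline, and name the T4 contrast as the primary effect. State in advance a fallback if the model does not converge, for example heterogeneous Toeplitz with robust standard errors.

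Use the same structure for the mixed-model estimates of the continuous secondary outcomes in section 10.2. The Seemingly Unrelated Regression test needs no change on this account.

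Cost: a few lines in section 10.1, repeated in the SAP, and no new data. An unstructured matrix over three visits has six parameters (three variances, three covariances) against two for a random intercept, so four more, which 212 participants can carry. The T4 interval may come out somewhat wider or narrower than under the random intercept, depending on the data.
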